In the second project year we will scale up the peer educators and mobile phone technology to assess whether these interventions are sustainable, effective and appropriately cost effective. Qualitative studies will assess provider and patient attitudes towards these interventions.

Methods:

Study Design and Rationale

Research Design and Methods

Overview: A pilot peer educator/mobile phone intervention suggest that these programs are realistic in this resource-limited setting. However, there has been insufficient time and funding to assess the impact of these services on patient adherence and virologic outcomes. This proposal aims to build upon these early studies by:

- Extending the cluster-randomized peer educator and mobile phone programs for a one year study period in order to better assess impact on virologic treatment failure and adherence. Secondary outcomes include CD4 count changes, mortality, and morbidity...
- 2) If a positive impact is demonstrated during the first project year, we will scale-up the peer educator and mobile phone interventions to all communities in order to evaluate the effects on compliance and virologic outcomes after introduction of services, compared to the prior time period. These interventions will be further evaluated by an analysis of cost and sustainability.

Three Arm Cluster-Randomized Operations Research Study:

Study Design and Population: The program will continue with the current three armed randomization scheme of 6 clinics with peer educators but no mobile phones (Arm A), 4 clinics with peer educators and mobile phones (Arm B), and 5 clinics with no peer

educators. We will maintain a ratio of 15-20 patients per peer educator. New peer educators will be recruited and trained as necessary to maintain this patient ratio. Outcomes will be compared between clinic patients in the peer educator arms compared to the control arm, as well as between patients in clinics with peer educators equipped with mobile phones compared to clinics with peer educators without mobile phones, or the control condition. All analyses will use de-identified data. The study population will be ~1000 PEPFAR patients enrolled in the RHSP ART program by March, 2007. Process data will be collected on intervention implementation. Provider evaluations will be done via PEPFAR staff and peer educator surveys.

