Please note all patient records are routinely collected for clinical care so no additional consent is required and there is no risk to patients entailed by the evaluation, since deidentified data will be used.

Study Outcomes: The primary outcomes will be virologic failure (defined as viral load >400 copies/ml), and ARV adherence as measured by pill counts percentage (sum of ARV pills taken/sum of ARV pills prescribed). Secondary outcomes include change in CD4 count from baseline, morbidity (new opportunistic infection or drug toxicity), and mortality. These outcomes are recorded in clinical records and will be abstracted, and stripped of identifiers for analysis.

Data Collection: Patient Data: As part of the clinical service, viral loads are assessed every six months and CD4 counts every three months for one year, and then every six months thereafter through PEPFAR clinical monitoring and a parallel NIH funded R01 study to evaluate the ARV effects on HIV epidemiology and behaviors (1R01HD050180; PI [name]). Data on ARV adherence will be derived from peer educator home visit records and pill counts at the bi-weekly clinic visits as part of the routine clinical service. Morbidity outcomes and descriptive data (gender, age, WHO stage, Karnofsky score) will be collected through clinic records and questionnaires administered by ARV clinic staff to patients initiating ART, weekly for the first month, and then at 3, 6, 9, 12, and 24 months on ART. These are routinely collected data and do not add a research burden. Mortality data will be collected through verbal autopsy interviews with relatives and friends of deceased patients. This is routinely done as part of the Rakai cohort study. Mobile phone data will be captured in real-time with an automated, preprogrammed SMS system. This mobile phone intervention will use locally available phones and technology.

Additional operational evaluation procedures for Peer Educators:

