1) Every six months, a questionnaire with a Likert scale (ordinal scale graded from 1 to 5, e.g 1=Strongly Agree, 5=Strongly disagree) and free text (unstructured response) questions will be administered to the PEPFAR staff and peer educators on their impressions of the intervention and suggestions for improvement. 2) Peer educators will be required to demonstrate knowledge and skills with an oral and practical test following bimonthly, one-day continuing education sessions. 3) RHSP field staff will perform spot checks of peer educator home visits during the initial 2 months of implementation. 4) Peer educator home visit forms will be entered into an electronic database and descriptive statistics compiled. This is an ongoing evaluation of personnel for QA/QC purposes.

Population:

Sample Size

The total number of PEPFAR patients expected to be enrolled by May 2007 is \sim 1000, so we anticipate \sim 330 patients in each of the three study arms. We already have \sim 6 months follow up information on \sim 800 patients in the pilot study. With a further one year follow up we will have information over \sim 18 months. Assuming a 5% drop out rate, we anticipate \sim 5,643 person months (\sim 470 py) per study arm. Detectable viral load (i.e., virologic failure) is \sim 28%. ¹²

Power Calculations or Statistical Plan

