This is an unmatched community randomized study. However, the Rakai communities have been selected to be homogeneous, and prior estimates indicate a coefficient of variation (k) between clusters of 0.24. Thus, design effects are modest (\sim 1.26). With a two-sided α = 0.05 and 1-β of 0.80, the study will have the power to detect a reduction in virologic failure in either intervention arm relative to the control arm with rate ratio (RR) \leq 0.70 (i.e., a failure rate ≤ 19.6%). If the two peer educator intervention arms are compared to the control arm, the study will have a power to detect a reduction in virologic failure of RR ≤ 0.74 (i.e. ≤ 20.7%). Descriptive analyses will compare patients in each study arm at time of enrollment with respect to sociodemographic characteristics, WHO stage, viral load, CD4 count and Karnofsky score. Univariate analyses will assess outcomes by strata of covariates in each intervention arm. For dichotomous outcomes (e.g., virologic failure, drug toxicity, OIs, and mortality) we will use multivariate log-binomial regression to estimate the relative risk of treatment failure, adherence etc. between intervention arms, adjusted for covariates found to differ between arms at p < 0.15 in univariate analyses, or suspected confounders. Adjustment for clustered data will use general estimating equations (GGE) to estimate robust variances. For continuous data (e.g., adherence percent, CD4 changes from baseline to follow-up, number of drug toxicity events) we will use tests and analysis of variance (ANOVA). The effects of peer educators and mobile phone interventions will be assessed by stratified analyses and by interaction terms. The number of treatment failures prevented will be estimated.

Inclusion and Exclusion Criteria

Inclusion in the study is determined by receipt of ARVs in the PEPFAR program. This protocol however deals only with the analysis of de-identified data and the intervention received by subjects takes place under a different service program.

Gender, Age and Locale

Both males and females between ages <1 and 60 are included.

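### Adherence percent (co-primary) and CD4 change are assigned to tests and ANOVA with no cluster term although clinics are randomised; on patients treated as independent, error exceeds 5% by an amount the protocol does not fix

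*Protocol*

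**What the plan says.** - **Design.** Protocol, Power Calculations or Statistical Plan: "This is an unmatched community randomized study". Under Study Design and Population the allocation is "6 clinics with peer educators but no mobile phones (Arm A), 4 clinics with peer educators and mobile phones (Arm B), and 5 clinics" without peer educators, so 15 clinics in all.
- **Outcome.** Study Outcomes names two primary outcomes, virologic failure and "ARV adherence as measured by pill counts percentage". CD4 change is secondary.
- **Dichotomous outcomes.** The statistical plan uses log-binomial regression "to estimate the relative risk of treatment failure, adherence etc. between intervention arms". The next sentence says that clustered data will be adjusted for by GEE with robust variances.
- **Continuous outcomes.** The sentence after that reads, in its main part: "adherence percent, CD4 changes from baseline to follow-up, number of drug toxicity events) we will use tests and analysis of variance". It names no clinic term, no robust variance and no unit of analysis.
- **Error rate.** The power statement is made "With a two-sided α = 0.05 and 1-β of 0.80".

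**The concern.** In a cluster-randomised trial the arm comparison has to be judged against variation between clinics. An ordinary t test or ANOVA on patients judges it against variation between patients and treats about 1000 people as independent when only 15 units were randomised. The method named for a primary outcome would then give standard errors that are too small and p-values that are too low.

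The plan is also unsettled on which adherence analysis is primary. Adherence has a relative risk from a model that sits next to the cluster adjustment, and a percentage comparison that does not. The two could disagree, and the protocol does not say which one counts.

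Study Design and Rationale makes scale-up to all communities depend on a positive impact in the first year. It does not say which outcome or test decides this, but adherence is one of the two primary outcomes.

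**Working it through.** **Inputs from the protocol.** 15 clinics (6/4/5). About 1000 patients, so m = 1000/15 = 66.7 per clinic. Control virologic failure p = 0.28. Between-cluster coefficient of variation k = 0.24, with the outcome it describes not named. Stated design effect 1.26. Two-sided α = 0.05.

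**Not in the protocol.** Any ICC or between-clinic variation for adherence percent or CD4 change. Every error rate below therefore depends on an assumed ICC.

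**Step 1: the stated design effect.**
- ICC = k²p/(1−p) = 0.24² × 0.28/0.72 = 0.0224.
- DE = 1 + (m−1) × ICC = 1 + 65.7 × 0.0224 = 2.47.
- The stated 1.26 is not reproduced. It would need about 12.6 patients per cluster, since 1 + 11.6 × 0.0224 = 1.26, or, with 66.7 per clinic, an ICC of 0.26/65.7 ≈ 0.004.

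That mismatch is a separate matter. Here it means that two design effects, 1.26 and 2.47, can each be traced to the protocol, and both are carried forward.

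**Step 2: false-positive rate of an unadjusted patient-level analysis.**
- Two-arm test: 2 × [1 − Φ(1.96/√DE)].
- Three-arm ANOVA (large-sample, 2 df): P(χ²₂ > 5.99/DE) = exp(−5.99/(2·DE)).

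| Assumption for adherence | DE | Two-arm test | Three-arm ANOVA | SE too small by √DE |
|---|---|---|---|---|
| Stated design effect (ICC ≈ 0.004) | 1.26 | 8.1% | 9.3% | 1.12 |
| ICC 0.01 | 1.66 | 12.8% | 16.4% | 1.29 |
| ICC 0.0224 (from k and 28%) | 2.47 | 21.2% | 29.7% | 1.57 |
| ICC 0.05 | 4.28 | 34.4% | 49.7% | 2.07 |

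Worked case at DE 1.26: 1.96/1.122 = 1.746, giving 8.1%; exp(−5.99/2.52) = 9.3%.

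**Step 3: simulation.** With 20,000 simulated null trials of 6/4/5 clinics, the patient-level tests gave about 8% and 9% at ICC 0.004, 12 to 14% and 16 to 17% at ICC 0.01, and 20 to 23% and 30% at ICC 0.0224. The ranges cover 67 patients in every clinic and, alternatively, about 330 patients per arm. Unequal arm sizes hardly matter.

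**Step 4: the remedy.** In a further 20,000 simulated null trials per setting, a t test on unweighted clinic means rejected 4.4 to 5.3% of the time. This covered all three arm pairs and both peer-educator arms pooled against control, ICCs from 0.004 to 0.05, and both sets of clinic sizes. Degrees of freedom are 6+5−2 = 9, 4+5−2 = 7, 6+4−2 = 8, and 10+5−2 = 13 pooled.

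**The case against.** The strongest reply is that the protocol never says clustering is ignored. The GEE sentence stands on its own, is not limited to dichotomous outcomes, and GEE works for continuous outcomes too. The plan declares a community-randomised design and quotes a design effect. The Peer Educator Intervention Description says the data are analysed by community of randomisation. Adherence also appears under the log-binomial model, so at least one adherence analysis may be cluster-adjusted.

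Much of this stands. A reader might infer that the protocol deliberately discards the clinic randomisation for adherence, and the text does not support that. What it supports is that the named method has no cluster term and the adjustment is not clearly extended to it. The generous reading does not remove the problem: ordinary tests and ANOVA carry no GEE robust variance, so the continuous-data sentence cannot be followed as written and be adjusted at the same time. The remark about community of randomisation sits in a note on consent and de-identified data and names no method.

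A reader might also infer that the false-positive rate is 20 to 30%, or that standard errors are too small by half. Neither is a fact of the document. Those figures need an ICC derived from a binary outcome to hold for a pill-count percentage. The protocol's own design effect gives 8 to 9% and a factor of 1.12.

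The adherence cut-off and person-time for toxicity counts can be left to a statistical analysis plan. Change from baseline is a legitimate CD4 analysis.

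**Conclusion.** The point holds in this form. For the continuous co-primary outcome and for CD4 change, the only methods named are tests and ANOVA with no cluster term, in a trial of 15 randomised clinics. Applied to patients as independent, they exceed 5% at any positive ICC.

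The size is conditional. Between the two design effects traceable to the protocol, it runs from about 8% to 21% for a two-arm test and from 9% to 30% for the three-arm ANOVA, with standard errors too small by about 1.1 to 1.6. A larger adherence ICC would make it worse and a smaller one milder. These figures assume about 67 patients per clinic and a patient-level analysis.

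The listing of adherence under two analyses needs no ICC and should be settled in any case. A protocol that chooses a method for a primary outcome should choose one that is valid for its design, so this should be corrected before analysis.

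**What to change.** In the statistical plan, replace tests and ANOVA for continuous outcomes by an analysis that respects the clinic. Either:

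- compute each clinic's mean, or its mean covariate-adjusted residual, and compare arms by t tests on those summaries (9 df for peer educators without phones against control, 7 for peer educators with phones against control, 8 between the two peer-educator arms, 13 for both pooled against control); or
- fit a mixed model with a clinic random effect and small-sample degrees of freedom.

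Name adherence percent, as defined under Study Outcomes, as the single primary form, and make any dichotomised version secondary. Optionally, include baseline CD4 as a covariate in the CD4 model.

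This needs no new data and no more patients. The cost is wider confidence intervals and less apparent power for adherence, because 7 to 13 degrees of freedom is what 15 clinics provide.
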